4.0 OVERVIEW OF STUDY DESIGN/INTERVENTION

4.1 Design

This is a Phase I single-arm feasibility study of multi-beam IMRT with daily set-up verification in the treatment of women with node-positive breast cancer who will receive radiation to the breast/chest wall and regional lymph nodes, including the internal mammary lymph nodes.

4.2 Intervention

IMRT with multiple beams will be utilized to treat the breast or chest wall and axillary, supraclavicular and internal mammary lymph nodes. Treatment will be delivered once a day, 5 days a week for approximately 5 weeks. Daily set-up error will be checked prior to the delivery of every treatment.

Prior to beginning treatment with multi-beam IMRT, patients will be status post partial mastectomy or mastectomy with an assessment of axillary lymph node status. Axillary assessment may be any combination of sentinel lymph node biopsy or axillary lymph node dissection.

Concurrent cytotoxic chemotherapy is not allowed in this study. Concurrent biologic therapy with radiation therapy is allowed. We anticipate that concurrent trastuzumab will be the most frequent example of concurrent biologic therapy. Antiestrogen hormonal therapy (eg, Tamoxifen or aromatase inhibitors) may be administered concurrently with radiation therapy.

5.0 THERAPEUTIC/DIAGNOSTIC AGENTS

5.0.1 Two techniques that allow verification of setup accuracy are currently available in the Department of Radiation Oncology:

1) AlignRT employs three ceiling-mounted 3D camera units to produce high-resolution and accurate 3D surface data referenced to the treatment isocenter. At each treatment fraction, the system images the current patient position instantaneously. AlignRT® is able to gate its image capture so that 3D data are acquired at a reproducible point in the breathing cycle. State-of-the-art surface-matching software registers these data to the reference surface within seconds. Couch shifts are displayed to show discrepancies between existing and ideal treatment positions. New coordinates for the optimal couch position are then displayed and may be applied. This system has been FDA approved. Further information regarding this approval is available on the website http://www.visionrt.com/site_files/AlignRT%20SE%20FDA%20Clearance%20Letter.pdf.

2) An orthogonal pair of KV images allows optimal visualization of bony anatomy as well as clips in the lumpectomy cavity or axilla. One Trilogy and two 2100EX linear accelerators with on-board KV imagers are available in the department.

5.0.2 BreastQ questionnaire

The BreastQ questionnaires have been developed by the MSKCC Department of Surgery. For patients who received a mastectomy with or without reconstruction, the questionnaire will be administered at baseline and 5-7 months after treatment (Appendix 6). Below is information about the questionnaire validation process:

The conceptual model and item list were developed from patient interviews (n=48), focus groups (n=18), expert panels and literature review. A conceptual model for the impact of breast surgery was developed with scales that examine: (1) psychosocial well-being, (2) physical well-being, (3) sexual well-being, (4) satisfaction with breasts, (5) satisfaction with overall outcome and (6) satisfaction with care. The process of item generation led to a separate module for each surgery type: 1) breast augmentation, 2) reduction, 3) reconstruction and 4) mastectomy without reconstruction. Each module has a pre and postoperative version with all preoperative items repeated in the postoperative questionnaires. . The preliminary questionnaire was pilot tested with cognitive debriefing interviews

(n=47) and further modified. Field-testing was performed at 5 centers in the US and Canada (total n=1950, test-retest n=491, response rate 72%). Item response theory (Rasch) analysis was used for item reduction and scale development. In the item reduction analysis, 48% of field-test items were eliminated. Cronbach's alphas for all 18 scales (3 modules with 6 scales) ranged from 0.87 to 0.98. Test-retest reliability, as measured by intraclass correlation coefficients, ranged from 0.85 to 0.98. Validation studies examining convergent and discriminant validity of the new measure relative to multiple existing measures (i.e. EORTC BR-23, BIS, BEQ, SF-36, PAR, BIBCQ, BSAS) are currently underway.

6.0 CRITERIA FOR SUBJECT ELIGIBILITY

6.1 Subject Inclusion Criteria

1. Female gender
2. Age \geq 18 years
3. An invasive primary breast cancer of any histology arising from breast parenchyma
4. Patient must be status post mastectomy or partial mastectomy with an assessment of axillary nodes via sentinel lymph node biopsy and/or axillary lymph node dissection
5. Pathologic confirmation of metastatic disease in at least one regional lymph node. Regional lymph nodes are defined as the ipsilateral axillary lymph nodes, ipsilateral supraclavicular lymph nodes, and ipsilateral internal mammary lymph nodes. Thus, any T stage is allowed as long as the N stage is \geq 1 and M stage is 0.
6. Patient signed study-specific consent form.

6.2 Subject Exclusion Criteria

1. Patients with distant metastasis.
2. Patients who are pregnant or breastfeeding.
3. Patients with psychiatric or addictive disorders that would preclude obtaining informed consent.
4. Time between initial diagnosis of breast cancer and start of radiation therapy exceeds 13 months.
5. Estimated life expectancy judged to be less than one year by patient's treating radiation oncologist.
6. Prior radiation therapy to the ipsilateral or contralateral breast or thorax.
7. Primary breast cancer is a lymphoma or sarcoma histology.
8. Patients with a history of non-skin malignancy $<$ 5 years prior to the diagnosis of breast cancer.
9. Patients requiring radiation to the bilateral breasts

7.0 RECRUITMENT PLAN (Limited Waiver of Authorization)

This study will be available to all patients seen at MSKCC who meet the eligibility criteria. MSKCC is a large referral center for breast cancer. In addition, the study will be placed on the MSKCC Website as well as available at the MSKCC satellite centers to maximize patient recruitment. Patients will be identified at consultation in the Radiation Oncology clinics for their eligibility. The investigators take due notice of the National Institutes of Health (NIH) policy concerning inclusion of women and minorities in clinical research populations.

Potential research subjects will be identified by a member of the patient's treatment team, the protocol investigator, or research team at Memorial Sloan-Kettering Cancer Center (MSKCC). If the investigator is a member of the treatment team, s/he will screen their patient's medical records for suitable research

study participants and discuss the study and their potential for enrolling in the research study. Potential subjects contacted by their treating physician will be referred to the investigator/research staff of the study.

The principal investigator may also screen the medical records of patients with whom they do not have a treatment relationship for the limited purpose of identifying patients who would be eligible to enroll in the study and to record appropriate contact information in order to approach these patients regarding the possibility of enrolling in the study.

During the initial conversation between the investigator/research staff and the patient, the patient may be asked to provide certain health information that is necessary to the recruitment and enrollment process. The investigator/research staff may also review portions of their medical records at MSKCC in order to further assess eligibility. They will use the information provided by the patient and/or medical record to confirm that the patient is eligible and to contact the patient regarding study enrollment. If the patient turns out to be ineligible for the research study, the research staff will destroy all information collected on the patient during the initial conversation and medical records review, except for any information that must be maintained for screening log purposes.

In most cases, the initial contact with the prospective subject will be conducted either by the treatment team, investigator or the research staff working in consultation with the treatment team. The recruitment process outlined presents no more than minimal risk to the privacy of the patients who are screened and minimal PHI will be maintained as part of a screening log. For these reasons, we seek a (partial) limited waiver of authorization for the purposes of (1) reviewing medical records to identify potential research subjects and obtain information relevant to the enrollment process; (2) conversing with patients regarding possible enrollment; (3) handling of PHI contained within those records and provided by the potential subjects; and (4) maintaining information in a screening log of patients approached (if applicable).

We estimate that between 130 and 150 eligible patients are treated in the Department of Radiation Oncology per year. On average, 15-20 eligible patients are under treatment at any moment. This provides a large pool of patients who could be eligible for this study. We estimate that, on average, there will be room for approximately five to ten breast cancer patients on our treatment machines, leading to treating 30-60 breast cancer patients per year. Considering these estimates, we predict that we will meet our accrual goal of 100 evaluable patients within two years. Patients will be considered evaluable when they have completed their 5-7 month follow-up and PFT. Patients that have been registered but have withdrawn from the study prior to completing their 5-7 month follow-up and PFT will not be evaluable for the study. Since there may be patients enrolled on study who are later found to be inevaluable, our maximum target accrual is 120 patients. However, if we are able to accrue 100 evaluable patients before we reach the maximum target accrual, we will close the study to accrual.

8.0 PRETREATMENT EVALUATION

All of the following pretreatment evaluations should be completed within 45 days of the start of radiation therapy:

- Assessment of weight and height for calculation of BMI
- Completion of the CAP questionnaire
- Completion of the BreastQ (if patient received mastectomy +/- reconstruction)
- PFTs
- Serum pregnancy test (for women of childbearing potential)

- Attestation that an acceptable radiotherapy treatment plan has been generated. Guidelines defining a dosimetrically “acceptable” radiation plan are described in Section 9.3 and 9.4. The treating radiation oncologist must confirm whether an acceptable multi-beam IMRT plan was generated or not by signing the patient’s treatment plan. If an acceptable plan cannot be generated then the patient is scored as a failure for feasibility purposes and is no longer in this study
- Mammogram (any time prior to treatment. Only applicable for patients with intact breasts)
- History and physical exam in Radiation Oncology (no more than 120 days prior to the start of radiation therapy)

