10.0 EVALUATION DURING TREATMENT/INTERVENTION

Tests and Observation	Pre-Treatment	During IMRT	Completion of IMRT (CoT) ⁴	6-12 weeks after CoT	5-7 mo after CoT	Follow up ¹
History	X ²			X	X	X
Physical	X ²	X ⁵	X	X	X	X
(Feasible Plan Generated/Delivered)	X					
Daily Setup Data			X			
PFTs	X				X	
BMI	X					
Mammogram ³	X					X
Clinical Assessment of Acute Skin Toxicity		X ⁵	X	X		
Late Subcutaneous Fibrosis					X	X
Late Cutaneous Toxicity					X	X

Clinical Assessment of RP				X	X	X
RP CAP Questionnaire	X			X	X	X
BreastQ Questionnaire (for mastectomy patients)	X				X	
Pregnancy test (if relevant)	X					
¹ Patients will be seen at 12-14 months following the CoT and then every 6-8 months for up to 5 years of follow up. ² Done within 120 days of RT start ³ Mammogram at baseline and then annually or more often if clinically indicated (only applicable for lumpectomy patients). The annual mammogram will be based on the patient's last follow up mammogram (+/- 1 month window). For patients found to have distant metastasis after treatment, annual mammograms will no longer be required. ⁴ Done ±10 days of the last radiation treatment (CoT) ⁵ Done at least two times during radiation treatment including the CoT timepoint						

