10.1 Evaluations During Treatment

All patients will undergo an interview and physical examination a minimum of two times during radiation treatment. The maximum toxicities graded by CTCAE will be submitted to the Research Study Assistant at the Completion of IMRT Treatment (CoT). CoT is defined as within ten days of the last radiation treatment.

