11.0 TOXICITIES/SIDE EFFECTS

Patients will be assessed for toxicities related to radiation treatment. Potential acute side effects include skin reactions, erythema, edema, hyperpigmentation, desquamation, fatigue, and/or RP. The incidences of these side effects with conventional radiation techniques to the breast and lymph nodes are described in Section 3.2.1.

Lactating and pregnant women are also excluded because of potential teratogenic effects of radiotherapy that may be harmful to the developing fetus or nursing infant.

Patients will be assessed for late toxicities (>3 months post radiation) as described in Section 3.2.2, including skin toxicity and/or RP. Toxicities will be scored according to the CTCAE, version 3.0 criteria.

No side effects are expected to result from the daily imaging used for target localization.

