12.2 Assessment of Secondary Objectives

Various metrics will be gathered at the following times: Pre-treatment (defined as within 45 days prior to the start of radiation treatment, excluding the History and Physical and mammogram), completion of therapy (done \pm 10 days of the last radiation treatment), 6-12 weeks following CoT, 5-7 months following CoT, and 12-14 months following CoT. These metrics are described below.

a. To evaluate the rate and severity of both acute and late cutaneous toxicity

The radiation oncologist will score cutaneous toxicity at the end of treatment (\pm 10 days of the last radiation treatment) and at 6-12 weeks following CoT. Late cutaneous toxicity will be scored at 5-7 months and 12-14 months following CoT, utilizing the CTCAE version 3.0 grading system. Some of these toxicities are not appropriately measured by the CTCAE and a more suitable scale is attached in Appendix 2.

b. To evaluate the rate and severity of late subcutaneous fibrosis

The radiation oncologist will score late subcutaneous fibrosis at 5-7 months and 12-14 months following CoT, utilizing the CTCAE version 3.0 grading system. Some of these toxicities are not appropriately measured by the CTCAE and a more suitable scale is attached in Appendix 2.

c. To evaluate the rate and severity of RP.

RP rates will be assessed by CTCAE version 3.0 grading system at 6-12 weeks, 5-7 months and at 12-14 months following CoT. We will also administer the CAP questionnaire pretreatment, at 6-12 weeks, 5-7 months and at 12-14 months following CoT. PFTs will be obtained at pretreatment and 5-7 months following CoT.

d. To evaluate local-regional control rates

Locoregional recurrence is defined as tumor in the ipsilateral breast/chest wall and/or ipsilateral regional lymph nodes (axillary, supraclavicular or internal mammary). Time to local recurrence will be calculated from the date of the completion of radiation treatment to the date of the biopsy proving recurrence or the first CT, PET, or MRI scan demonstrating recurrence. Kaplan-Meier methods will be used to assess local-regional control.

e. To evaluate patient set-up reproducibility in breast cancer patients treated with multi-beam IMRT using daily 3D position verification.

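### The only scheduled pregnancy test may be 45 days old at the first fraction, so the protocol's own check need not confirm the pregnancy exclusion when treatment begins

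*Combined protocol and SAP*

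**What the plan says.** Section 8.0 opens its list of baseline assessments with a common rule: "All of the following pretreatment evaluations should be completed within 45 days of the start of radiation therapy". One item on the list is "Serum pregnancy test (for women of childbearing potential"), with no timing of its own. Two other items do carry their own timing. The mammogram may be done at any time before treatment, and the history has a longer limit: "History and physical exam in Radiation Oncology (no more than 120 days prior to the start of radiation therapy").

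Section 12.2 restates the pre-treatment window as "defined as within 45 days prior to the start of radiation treatment, excluding the History and Physical and mammogram". The pregnancy test is not among those exceptions, so the 45 days apply to it there too.

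The Section 10.0 table has a row "Pregnancy test (if relevant") with a single mark, in the pre-treatment column. The history and physical have a timing footnote; the pregnancy test has none.

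Section 6.2 excludes "Patients who are pregnant or breastfeeding". Section 11.0 gives the reason: "Lactating and pregnant women are also excluded because of potential teratogenic effects of radiotherapy that may be harmful to the developing fetus". Section 17.0 repeats it.

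**The concern.** The exclusion rests on fetal harm from radiotherapy, so the relevant fact is whether the woman is pregnant when therapeutic exposure starts. The plan times the one objective check of that fact as if it were a stable baseline measure such as BMI or lung function. A woman can test negative, conceive, and receive her first fraction with every protocol requirement met.

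Women of childbearing potential are within the target population. Section 6.1 admits patients from age 18, Section 3.1 names premenopausal status among the factors favouring comprehensive radiation, and the protocol itself judged a test necessary. The stake is participant safety. No statistical result depends on it.

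**Working it through.** The plan states no figure to reproduce. The check is a reading of every place that could verify pregnancy status, followed by calendar arithmetic.

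**Could another scheduled check cover the gap?**

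| Place | What it provides | Does it confirm status near fraction 1? |
|---|---|---|
| Section 8.0, pregnancy test | One serum test, up to 45 days before the start | Not required to |
| Section 8.0, history and physical | Up to 120 days before the start; may precede or follow the test | Not required to |
| Section 15.1, eligibility checklist | Confirmation at registration, with no stated timing relative to fraction 1 | Not required to |
| Section 10.1, on-treatment visits | "All patients will undergo an interview and physical examination a minimum of two times during radiation treatment" | No; these follow first exposure |
| Section 13.0, removal from study | Removes a patient found ineligible at any time | No; it schedules nothing that would find her |

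In the text supplied, the single serum test is therefore the only scheduled objective check, and nothing ties it closely to fraction 1.

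**Inputs**

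- Outer limit for the test: 45 days before the start (Sections 8.0 and 12.2).
- Course: 25 fractions (Section 9.3.2), once a day, 5 days a week (Section 9.5.1).
- Assumed here: no missed visits and no boost.

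**Maximum age of the test at fraction 1**

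45 days; 45 / 7 = 6.4 weeks.

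**Maximum age at fraction 25**

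Fraction 25 comes 24 treatment days after fraction 1. Twenty of these make four calendar weeks (28 days), and four weekdays remain.

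- Monday start: the four weekdays cross no weekend, so 28 + 4 = 32 days.
- Tuesday to Friday start: they cross one weekend, so 28 + 6 = 34 days.

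The ceiling at fraction 25 is 45 + 32 = 77 to 45 + 34 = 79 days.

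**Effect of a shorter window**

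The documents give no basis for a particular number of days, so the windows below other than 45 are assumptions.

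| Window (days) | Ceiling at fraction 1 | Ceiling at fraction 25 |
|---|---|---|
| 45 (current) | 45 | 77–79 |
| 28 | 28 | 28 + 32 = 60 to 28 + 34 = 62 |
| 14 | 14 | 14 + 32 = 46 to 14 + 34 = 48 |
| 7 | 7 | 7 + 32 = 39 to 7 + 34 = 41 |

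The fraction-1 column is the one that bears on the exclusion. The fraction-25 column only adds the length of the course and is shown for completeness. All entries are ceilings on test age and do not estimate missed pregnancies.

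**The case against.** The strongest reply is that nothing in the plan is inconsistent. Sections 8.0, 10.0 and 12.2 agree, the documents cite no standard that 45 days breaches, and sites may well test nearer to treatment. Radiotherapy departments may also screen for pregnancy as routine. Section 9.1 says that simulation generally follows standard departmental procedure, and the consent pages, which might contain pregnancy warnings or a duty to report, are not available here. These women need comprehensive radiotherapy in any case, so pregnancy screening is partly a matter of clinical care and the trial is not shown to add fetal risk.

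Much of this stands as a limit on importance. Whether a gap exists in practice cannot be settled from these documents, and no claim is made about contraception advice. It does not remove the point. The plan states an explicit rule which, followed exactly, can leave one of its own exclusions unverified at first exposure. An exclusion justified by fetal harm should be verifiable from the protocol's own schedule.

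A second reply concerns the remedy. Simulation, contouring, planning and plan approval all come before fraction 1, and the documents do not say how long they take. If they take longer than the new window, a single test anchored to fraction 1 would have to fall after the CT simulation. The present wording permits that order too, but a short window could force it. This is a fair caution, and it is the reason for the optional history check before simulation. A shorter window also narrows the gap without closing it.

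**Conclusion.** The point holds, as a minor patient-safety improvement. A compliant pregnancy test can be up to 45 days (6.4 weeks) old at the first fraction, and no other check close to that fraction is scheduled in the supplied text. The protocol's check therefore need not verify the exclusion when exposure begins; a test taken a few days beforehand would comply equally and would come much closer to doing so.

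The conclusion rests on the protocol text alone. It assumes nothing about departmental screening or consent wording, either of which could reduce or remove the practical gap. The number of women of childbearing potential, the usual interval from test to treatment and the chance of conception in that interval are not given; the number affected is probably small. The 100-patient sample size, the 90-of-100 rule and the planned confidence interval are unaffected.

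**What to change.** Take the serum pregnancy test out of the common 45-day window in Section 8.0 and give it its own short window before fraction 1. Fourteen days is offered as an example, an assumed figure for the sponsor to confirm against the usual planning time. Add the test to the exceptions in the Section 12.2 pre-treatment definition, and put a timing footnote on its row in the Section 10.0 table.

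Optionally, confirm pregnancy status by history before simulation and again before fraction 1, unless the department already does so. In that case, a sentence pointing to the departmental procedure would be enough for these history checks.

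The core change is one line, one exception and one footnote. It keeps the same single blood draw, and its cost is occasional rescheduling of that draw. The optional history checks would also need entries in Sections 9 and 10 and on the case report form.
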